**Figure 7. Schematic for Safety Management of ALT Elevation**

## 10 STATISTICAL CONSIDERATIONS

### 10.1 General Considerations

This section provides the key details of the statistical analyses to be performed using data captured according to this protocol. A complete Statistical Analysis Plan (SAP) describing all planned analyses will be finalized prior to database lock.

### 10.2 Determination of Sample Size

Cohort 1 will enroll virologically suppressed subjects on NrtI therapy with HBeAg negative cHBV. Approximately 60 subjects will be randomized to receive 1 of the following 3 treatments, VBR+AB-729+NrtI, VBR+NrtI, or AB-729+NrtI in a 2:1:1 ratio.

Up to 2 additional cohorts, with approximately 60 subjects per cohort, may be added in future protocol amendments, for a maximum sample size of approximately 180 subjects.

This is a proof-of-concept study. The sample size is similar to that previously utilized for this type of study and is not based upon statistical considerations.

### 10.3 Analysis Populations

The following populations will be considered for analysis of various endpoints:

- **Randomized Analysis Set:** It includes all randomized subjects who satisfied the inclusion and exclusion criteria described in this protocol.
- **Full Analysis Set:** It includes all randomized subjects, classified according to the treatment group into which they were randomized regardless of the actual treatment received, who took at least 1 dose of study drug. It is the main analysis population for the efficacy analysis.
- **Safety Analysis Set:** It includes all subjects, classified according to the actual treatment received regardless of random assignment, who took at least 1 dose of study drug. This is the main analysis population for all safety analyses.
- **Pharmacokinetic-Evaluable Set:** It consists of all subjects, classified according to the actual treatment received regardless of random assignment, who receive at least 1 dose of study drug. At least 1 pharmacokinetic blood sample following a dose of study treatment is required for inclusion in this analysis. This is the main analysis population for all pharmacokinetic analyses.

Based on the actual deviations, the criteria for exclusion of subjects from the different data sets will be specified and updated, if necessary, prior to database lock.

## 10.4 Planned Analyses

All safety, PK, and antiviral activity endpoints will be summarized using descriptive statistics by treatment groups. Continuous endpoints will be described using the mean, standard deviation, median, minimum, and maximum. Categorical endpoints will be described using the number and percent of subjects who meet the endpoint criterion.

Analyses by treatment group will be presented as follows:

- Efficacy analyses: according to the treatment to which subjects were randomized
- Safety and pharmacokinetic analyses: according to the treatment received

Due to sample size limitations, no formal statistical inference is planned.

### 10.4.1 Disposition of the Study Subjects

The disposition of subjects will be described with summaries by treatment group of the number of subjects in each analysis set described above, the number of subjects who completed the study, and the number of subjects for whom study drug was permanently discontinued (including the reasons for discontinuation). Randomized Analysis Set will be used to produce this analysis.

### 10.4.2 Demographic and Baseline Characteristics

Demographic and Baseline characteristics will be summarized using standard descriptive methods by treatment group and overall. Demographic summaries will include age, sex, race, ethnicity, body weight, and body mass index. Baseline disease characteristics data will include, but not limited to, years positive for HBV, HBV genotype, HBV DNA, HBV RNA, HBeAg, HBsAg, HBcrAg, and ALT levels at Baseline.

### 10.4.3 Extent of Exposure

Extent of exposure to study drug will be examined by assessing the total duration of study drug exposure and the level of adherence to the study drug by treatment group for the Safety Analysis Set.

### 10.4.4 Analysis of Efficacy Endpoint(s)

The efficacy endpoints are described in [Section 3.2.2](#). The efficacy analysis will be based on the Full Analysis Set.

In addition to the descriptive statistics at each time point, treatment comparisons may be performed. The continuous variables, such as mean change from Baseline, will be evaluated using a regression model with Baseline values and stratification as covariates. The binary variables, such as the proportion of subjects who meet the endpoint criterion, will be evaluated using a Cochran-Mantel-Haenszel test adjusting for the stratification factor.

#### **10.4.5 Analysis of Safety Endpoints**

All safety endpoints will be summarized using data from the Safety Analysis Set. Safety analyses will involve examination of the incidence, severity and type of TEAEs reported, changes from Baseline in laboratory test results and in vital signs to specified time points throughout the study, and concomitant medications use.

##### **10.4.5.1 Adverse Events**

Adverse events will be coded using the Medical Dictionary for Regulatory Activities (MedDRA). A TEAE will be defined as any AE that begins on or after the date of first dose of study drug through end of study (completion of follow-up period or “lost to follow-up”).

Summaries (number and percentage of subjects) of TEAEs by system organ class and preferred term will be provided by treatment group. Summaries will include all TEAEs, TEAEs considered related to study treatment by investigators, TEAEs by Grade, and SAEs. All AEs, emergent or nonemergent, will be listed by subject. Any TEAEs leading to premature discontinuation from the study intervention and serious TEAEs will be presented as a separate table or a listing.

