**Table 1. Overall Summary of Treatment-Emergent Adverse Events Through Week 24 (Study 211)**

Characteristic [n, (%)]	Vebicorvir+NrtI (N=92)
Any Treatment-Emergent AE a	42 (46)
Grade 1	26 (28)
Grade 2	14 (15)
Grade 3 or 4	2 (2)
Serious adverse events	0
TEAEs leading to study drug discontinuation b	0

Abbreviations: AE=adverse event; n=number of subjects with event; N=Number of subjects in the Safety population; NrtI=nucleos(t)ide analog reverse transcriptase inhibitor; TEAE=treatment-emergent adverse event.

Source: Study 211 [Table 6.1.1.1](#).

Data cut through 12 March 2020 including AE data for the first 6 months of exposure in Study 211.

Adverse events were graded according to Division of AIDS (DAIDS) criteria.

a Subjects with more than 1 TEAE were reported in the highest TEAE grade.

b One non-TEAE (began in Study 201) led to study drug discontinuation in Study 211.

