## **3.2 Study Endpoints**

### **3.2.1 Primary Endpoint**

The primary endpoint of Cohort 1 is:

- Proportion of subjects with AEs, premature treatment discontinuation due to AEs, and abnormal laboratory results

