## 9 ADVERSE EVENTS AND TOXICITY MANAGEMENT

### 9.1 Definition of Adverse Event

An AE is any untoward medical occurrence in a study subject administered a study drug regardless of the causal relationship with treatment.

An AE, therefore, can be any unfavorable and unintended sign, symptom, or disease temporally associated with participation in an investigational study, whether or not considered study drug related. In addition to new events, any increase in the severity or frequency of a preexisting condition that occurs after the subject signs the ICF for participation is considered an AE. This includes any side effect, injury, toxicity, or sensitivity reaction. AEs may also include complications associated with protocol mandated procedures.

An AE does not include the following:

- Medical or surgical procedures such as surgery, endoscopy, tooth extraction, and transfusion. The condition that led to the procedure may be an AE and must be reported.
- Preexisting diseases, conditions, or clinically significant laboratory abnormalities present or detected before the screening visit that do not worsen during the study
- Situations where an untoward medical occurrence has not occurred (eg, hospitalization for elective surgery, social and/or convenience admissions)
- Overdose without clinical sequelae
- Any medical condition or clinically significant laboratory abnormality with an onset date before the consent form is signed and not related to a protocol-associated procedure is not an AE. It is considered to be preexisting and should be documented on the medical history electronic Case Report Form (eCRF).

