#### **7.1.5. Treatment-Emergent Adverse Events**

##### **7.1.5.1. Definition of Treatment-Emergent Adverse Events**

Treatment-emergent adverse events (TEAEs) are defined as any AEs with an onset date/time equal to or after the study drug start date/time through end of study .

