#### **7.1.6. Summaries of Adverse Events and Deaths**

Treatment-emergent AEs will be summarized based on the Safety Analysis Set. Tables will be created per study phase (i.e. On-Treatment Phase, Off-Treatment Phase, and NrtI-Restart Phase).

A brief, high-level summary of the number and percentage of subjects who experienced at least 1 TEAE in the categories described below will be provided by treatment group. The brief summary will also include treatment-related TEAEs, treatment-related TE SAEs, and TEAEs leading to premature study discontinuation. All deaths observed in the study will also be included in this summary. In addition, a table for each category showing the number and percentage of subjects will be provided by PT and treatment group in descending order of total frequency:

- TEAEs
- TEAEs by severity grade
- TEAEs related to AB-729
- TEAEs related to VBR
- TE SAEs
- TE SAEs related to AB-729
- TE SAEs related to VBR
- TEAEs leading to premature study drug AB-729 discontinuation
- TEAEs leading to premature study drug VBR discontinuation
- TEAEs leading to study discontinuation
- TEAEs leading to death (ie, outcome of death)

- COVID-19 specific TEAEs
- COVID-19 specific TE SAEs

Multiple events will be counted only once per subject in each summary. For summary by severity grade, the most severe grade will be used for those AEs that occurred more than once in an individual subject during the study.

A data listing containing all AEs will be provided.

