#### **7.2.1.1. Treatment-Emergent Laboratory Abnormalities**

Treatment-emergent laboratory abnormalities are defined as values that increase at least 1 toxicity grade from Baseline at any postbaseline time point. If the relevant baseline laboratory value is missing, any abnormality of at least Grade 1 observed within the time frame specified above will be considered treatment emergent.

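### TEAEs are defined by onset alone and the drug-discontinuation tables count only TEAEs, so an AE that starts in Screening and later stops drug is left out of them

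*Combined protocol and SAP*

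**What the plan says.** The primary endpoint (protocol 3.2.1) is "Proportion of subjects with AEs, premature treatment discontinuation due to AEs, and abnormal laboratory results". It speaks of AEs, not TEAEs.

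Protocol 9.2 has AEs recorded from written consent to the end of the study. Screening takes up to 45 days (8.3.1) and can be extended (5.4).

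The protocol (10.4.5.1) defines a TEAE as "any AE that begins on or after the date of first dose of study drug", and the SAP (7.1.5.1) as "any AEs with an onset date/time equal to or after the study drug start date/time". Both run to the end of the study. Neither has a clause for worsening or for an AE that leads to stopping drug.

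SAP 7.1.6 builds its AE tables on TEAEs. One is headed "TEAEs leading to premature study drug VBR discontinuation", and there is a matching one for AB-729. Protocol 10.4.5.1 likewise confines its discontinuation display to TEAEs.

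Protocol 9.1 says that "any increase in the severity or frequency of a preexisting condition that occurs after the subject signs the ICF for participation is considered an AE". The laboratory rule in SAP 7.2.1.1 counts "values that increase at least 1 toxicity grade from Baseline at any postbaseline time point".

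**The concern.** An AE with onset between consent and first dose is collected but is not a TEAE. If it later causes the subject to stop VBR or AB-729, it meets the wording of a primary-endpoint component and is excluded by rule from the table for that component. If it rises in grade on drug, whether it is counted depends on how the site enters it, and the documents do not say how.

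The omission runs one way: the rule can lower the AE and AE-discontinuation counts but never raise them. Safety is the primary objective and two of the three groups have 15 subjects, so a single omitted case is visible. The report could also disagree with itself, with an AE-related stop in the disposition table and none in the AE-discontinuation table.

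**Working it through.** The plan gives no power calculation or derived sample size to reproduce. The check is therefore to trace each type of event through the rules and then to work out what one omitted subject is worth.

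**Step 1. Trace the cases.**

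| Case | TEAE? | Where it can still appear |
|---|---|---|
| Onset on or after first dose | Yes | TEAE tables |
| Condition present before consent, worsens after first dose | Yes: 9.1 makes the worsening an AE, with post-dose onset | TEAE tables |
| Onset between consent and first dose, grade rises on drug, entered as a new AE | Yes | TEAE tables |
| Same, kept as one record with its pre-dose onset | No | AE listing; graded laboratory tables if a laboratory value; disposition if drug is stopped; deaths if fatal |
| Onset between consent and first dose, no rise in grade, drug stopped because of it | No | Disposition (SAP 4.1) and AE listing |

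The last row is excluded under any way of recording. The fourth row depends on site entry, which protocol 9.2 refers to eCRF guidelines that are not in the documents. Section 9.1 does not settle it: it speaks of a preexisting condition and applies that term to "Any medical condition or clinically significant laboratory abnormality with an onset date before the consent form is signed", and an AE that began after consent is not one of those.

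**Step 2. Compare the neighbouring rules.** SAP 7.1.5.2 treats an AE with no dates at all as treatment-emergent, which is conservative. SAP 7.2.1.1 counts worsening of laboratory values from Baseline. The protocol's list of AE summaries names SAEs without qualification, while the SAP restricts them to treatment-emergent ones. A dated Screening AE that worsens or stops drug has no equivalent provision.

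**Step 3. Check the background study's table.** Protocol Table 1 (Study 211, N=92) is consistent: 26 + 14 + 2 = 42, and 42/92 = 45.7%, printed as 46%. The row for TEAEs leading to drug discontinuation shows 0, and the footnote says "One non-TEAE (began in Study 201) led to study drug discontinuation in Study 211". Counting any AE that led to stopping, the row would be 1/92 = 1.1%. An onset-only definition did move such a case out of the row and into a footnote.

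**Step 4. Weight of one subject here.** Planned groups are 60 × 2/4 = 30 and 60 × 1/4 = 15. The VBR row applies to Groups 1 and 2, the AB-729 row to Groups 1 and 3. Intervals are exact (Clopper-Pearson) 95%.

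- Group 1: 0/30 = 0% (0 to 11.6%) becomes 1/30 = 3.3% (0.1 to 17.2%).
- Group 2 or 3: 0/15 = 0% (0 to 21.8%) becomes 1/15 = 6.7% (0.2 to 31.9%).

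**The case against.** The best defence is that most of the safety information survives. Section 9.1 plausibly leads a site to record a post-dose worsening as its own AE, which is then a TEAE. SAP 4.1 tabulates non-completion of each drug with reasons, by group, with no TEAE filter. All deaths are summarised, all AEs are listed, and laboratory worsening is counted from Baseline. Overall AE incidence would seldom move, because most subjects will have some other TEAE. With the Study 211 rate and a constant hazard, about 1 − (50/92)² = 70% would have one by Week 48. These points stand. A reader might infer that such events vanish from every safety table, or that the whole primary endpoint is undercounted; the documents do not support either.

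Study 211 is also a limited precedent. The rash was disclosed, was Grade 1, began in the parent treatment study and not in an untreated Screening period, and is not shown to have risen in grade. It supports the change to the discontinuation rows and says nothing about worsening.

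Finally, one might carry the Study 211 AE rate into Screening. The hazard is −ln(1 − 42/92)/24 = 0.0254 per week, so over 45 days 1 − exp(−0.0254 × 45/7) = 15%, or 9 of 60. That is not an effect size. It counts subjects with any Screening-onset AE, applies an on-drug rate to an undosed period and assumes the full 45 days for everyone.

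None of this answers the discontinuation point. The table's TEAE restriction is a stated rule, and it is narrower than the endpoint.

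**Conclusion.** The point holds in limited form. A Screening-onset AE that leads to stopping VBR or AB-729 is left out of the SAP's TEAE and drug-discontinuation tables by definition. One that only rises in grade is left out of the TEAE tables unless the worsening is entered as a new AE.

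The consequence is a possible undercount in those tables and a possible mismatch with disposition, not a loss of the data. The mismatch assumes that an AE is among the recorded reasons for stopping, which the SAP does not list.

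The number of subjects affected cannot be derived from the documents and is probably small. Each is worth 3.3 percentage points in Group 1 or 6.7 in Group 2 or 3, at the planned group sizes. The change is worth making because the omission is one-directional and bears on the primary endpoint.

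**What to change.** 1. In SAP 7.1.6, base the VBR and AB-729 discontinuation rows on every AE that led to stopping that drug, regardless of onset. This needs no change to the TEAE definition and matches the endpoint.
2. In protocol 10.4.5.1 and SAP 7.1.5.1, extend the TEAE definition to an AE with onset before first dose whose grade increases on or after first dose. Apply this to the grade data already collected. Sites should not be asked to re-enter records: the SAP postdates the early termination, by which time all active subjects had finished the 48-week treatment period. If the database does not date a grade change, say so and apply the rule as far as the data allow.

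SAP section 1 provides for changes made after finalization to be documented in the Synoptic CSR, which is the place to record both. The cost is minor programming and possibly slightly higher AE counts.

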##### **10.4.5.2 Clinical Laboratory Evaluation**

Laboratory values will be graded according to DAIDS criteria ([Appendix 1](#)). Laboratory parameters will be summarized by treatment group at each visit. Incidence of graded laboratory abnormalities will be summarized by treatment group. Listings will be provided for clinical laboratory values for each subject grouped by laboratory panel.

##### **10.4.5.3 Other Safety Evaluations**

Individual data for physical examination findings, prior and concomitant medications and medical history will be provided. Vital signs measurements and 12-lead ECGs will be listed by subject and summarized by incidence of events/abnormalities or descriptive statistics as appropriate.

#### **10.4.6 Analysis of Pharmacokinetic Endpoints**

Population PK analysis may be performed outside the scope of this study.

Pharmacokinetic analysis of AB-729 for an optional intensive PK substudy will be conducted using the Pharmacokinetic-Evaluable Set defined in [Section 10.3](#). Plasma PK parameters of AB-729-AS and the AB-729-AS(N-1)3' and AB-729-AS(N-2)3' metabolites for each subject will be estimated over the sampling interval using noncompartmental analysis and summarized by treatment group using descriptive statistics. Plasma PK parameters to be estimated, as data allow, are listed below in [Table 13](#). Additional parameters may be analyzed, as appropriate. A minimum of 10 subjects from Group 1 and 5 subjects from Group 3 ([Figure 6](#)) will need to provide blood samples from Cohort 1 for PK analysis.

**Table 13. Pharmacokinetic Parameters and Definitions**

Parameter	Definition
$C_{max}$	maximum observed plasma concentration
$T_{max}$	time of maximum observed plasma concentration
$AUC_{0-t}$	area under the concentration time curve from the time of dosing to the last measurable concentration
$AUC_{TAU}$	area under the concentration time curve from the time of dosing to the end of the dosing interval
$C_{TAU}$	plasma concentration at the end of the dosing interval
$C_{trough}$	predose plasma concentration
AI	accumulation index for $AUC_{TAU}$ calculated as final dose/first dose

### **10.5 Interim Analysis**

No formal interim analyses are planned. As an open-label study, the data will be reviewed periodically.

### **10.6 Handling of Missing Data**

Statistical considerations and methodology for handling missing data will be detailed in the SAP.

### **10.7 Multiplicity Adjustment**

No formal inference is planned in this study; hence, no multiplicity adjustment is required.

## **11 RESPONSIBILITIES**

### **11.1 Investigator Responsibilities**

#### **11.1.1 Good Clinical Practice**

This study will be conducted in compliance with IRB/IEC and International Council for Harmonisation (ICH) Good Clinical Practice (GCP) Guidelines; Title 21 Part 56 of the US Code of Federal Regulations (CFR) relating to IRBs/IECs and GCP as described in the US FDA CFR (21 CFR § 50, 56, 312; China GCP; applicable ICH guidelines regarding clinical safety data management (E2A, E2B(R3))); European Community directives 2001/20, 2001/83, 2003/94 and 2005/28 as enacted into local law, and with ICH guidelines regarding scientific integrity (E4, E8, E9, and E10). In addition, this study will adhere to all local regulatory requirements, and requirements for data protection.

#### **11.1.2 Institutional Review Board (IRB)/Independent Ethics Committee (IEC)**

Before initiating a trial/study, the Investigator/institution must have written and dated approval/favorable opinion from the IRB/IEC for the study protocol/amendment(s), written ICF, any consent form updates, subject recruitment procedures (eg, advertisements), and any written information to be provided to subjects and a statement from the IRB/IEC that they comply with GCP requirements. The IRB/IEC approval must identify the protocol version as well as the documents reviewed.

#### **11.1.3 Informed Consent**

The Investigator will explain the benefits and risks of participation in the study to each subject or the subject's legally acceptable representative and obtain written informed consent. Written informed consent must be obtained prior to the subject entering the study and before initiation of any study-related procedure (including administration of investigational product).

The Sponsor or its designee will provide a sample ICF. The final, version dated, ICF must be agreed to by the Sponsor or its designees and the IRB/IEC and will contain all elements in the sample form, in language readily understood by the subject. Each subject's original consent form must be personally signed and dated by the subject or by the subject's legally acceptable representative, and by the person who conducted the informed consent discussion. The original, signed ICF will be retained by the Investigator. The Investigator will supply all enrolled subjects with a copy of their signed ICF.

The ICF may need to be revised during the study should important new information become available that may be relevant to the safety of the subject. In this instance approval should always be given by the IRB/IEC and existing subjects informed of the changes and reconsented. This is documented in the same way as previously described.

The Investigator should encourage subjects to inform their primary physician about their participation in the clinical study.

